9.4.2 ANALYSIS OF THE PRIMARY ENDPOINT(S)

Pain Intensity - The goal of this analysis is to test the effectiveness of PainTRAINER vs. EaseVRx in decreasing reported pain intensity. The trial will be a success if there is statistical evidence that either PainTRAINER or EaseVRx is more effective in reducing pain intensity. The primary outcome will be the baseline vs. week 8 difference-in-difference in 7-day average NRS pain intensity scores, dichotomized into if the MCID of 2 is achieved. The between arm difference of achieving the MCID of 2 will be tested using Chi-squared test.

- Additionally, we will use a logistic regression to determine whether the odds of achieving the MCID of 2 is different between the two groups after accounting for baseline-scores by including them as one of the predictors.

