1 PROTOCOL SUMMARY

1.1 SYNOPSIS

Title: Transcending COVID-19 barriers to pain care in rural America: Pragmatic comparative effectiveness trial of evidence-based, on-demand, digital behavioral treatments for chronic pain

Study Description: This study will compare two available, evidence-based, digital pain treatment programs that patients can use at home. The goal is to see if one approach is better than the other, and whether certain patients respond to one more than the other. Study participants will be randomized to receive one of two treatment programs: Skills-Based VR or PainTRAINER. Study devices will be delivered to the participant's home with instructions for use via FedEx; participants will receive remote technical support. They will be followed for 8 weeks and complete Patient Reported Outcome (PRO) questionnaires to assess functional status, pain levels, and use of pain medications (including opioids). Participants will also be asked to provide consent/authorization to access medical records from their treating facility.

[figure not shown]
Objectives: Primary Objective:
To compare the effectiveness of EaseVRx and PainTRAINER in improving perceived pain intensity from baseline to 8 weeks.

Secondary Objectives:

- To compare the effectiveness of EaseVRx and PainTRAINER in improving perceived pain catastrophizing over 8 weeks.
- To compare the effectiveness of EaseVRx and PainTRAINER in improving PROMIS anxiety over 8 weeks.
- To compare the effectiveness of EaseVRx and PainTRAINER in improving PROMIS pain interference over 8 weeks.
- To compare the effectiveness of EaseVRx and PainTRAINER in improving pain self-efficacy over 8 weeks.
- To compare the effectiveness of EaseVRx and PainTRAINER in reducing use of opioids over 8 weeks.

Endpoints:	Primary Endpoint: Daily Pain Intensity Secondary Endpoints: PROMIS Pain Interference, PROMIS Anxiety, Pain Catastrophizing, Pain Self-efficacy, and MME usage.
Study Population:	Individuals over age 13 with an ongoing pain problem that have experienced average pain intensity of >3 out of 10 within the previous 7 days.
Phase:	Phase 2
Description of Sites/Facilities Enrolling Participants:	Four outpatient clinic sites, including Cedars-Sinai Medical Center; Ochsner Medical Center; The University of Alabama at Birmingham; Bendcare Physician Network. In addition, participants may enroll remotely.

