4 STUDY DESIGN

4.1 OVERALL DESIGN

We will perform a two-arm RCT among a geographically diverse group of patients with mixed-etiology chronic pain. Using a random number generator, patients will be allocated in a 1:1 ratio at the site level between two self-administered, remotely deployed CBT delivery platforms: (1) a 2D mHealth app called PainTRAINER; and (2) 3D VR app called EaseVRx. The primary analysis will compare changes in pain intensity over 8 weeks upon completion of the standardized 8-week digital CBT protocols. Secondary outcomes will include pain catastrophizing, pain interference, self-efficacy, anxiety, and opioid use. Patient blinding is not possible in VR versus non-VR studies; we will explain the purpose of our study is to determine if one of two self-taught pain-management skills programs is more effective in helping manage pain, alongside current treatment. If so, how much more effective is it and which patients does the program help the most? Both programs have been proven effective; in other words, both programs have been studied and results for both showed improvement in patients' ability to manage their pain. To do this, participants will be randomly assigned to test either a virtual reality (VR) program called EaseVRx or an online/mobile program called painTRAINER. Because it is important for researchers to exhibit equipoise when describing the competing interventions, we will prepare a script that uses neutral language regarding the two interventions, as per previous VR research. In addition, data analysts will be blinded to patient allocation.

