6.3 MEASURES TO MINIMIZE BIAS: RANDOMIZATION AND BLINDING

We will allocate study participants using a random number generator to assign every-other patient to blocks of 2, 5, or 6 to ensure there is an equal distribution in the EaseVRx skills-based group and PainTRAINER group. Participants, their clinical providers, and study statisticians will be blinded to the study arm. The groups will be labeled as 1 or 0 at random. Datasets will be provided to the statistician using these group labels. A clinical research coordinator will ship VR headset containers to participants in the EaseVRx group and enter the label into the log of enrolled participants; the research coordinator who maintains the list of randomization assignments will not call participants on the telephone. Because the intervention is conducted in participants' homes and the data are collected remotely, the participants will not encounter each other and thus will be less likely to guess their study arm assignment. We anticipate there will be no circumstances during the study that require unblinding of an individual participant or a whole group because we do not expect any related SAEs to occur with this low risk intervention.

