9.4.3 ANALYSIS OF THE SECONDARY ENDPOINT(S)

Pain Interference, Pain Catastrophizing, Coronavirus-Related Anxiety, and Self-Efficacy

The goal of these analyses is to test the difference in the effectiveness of PainTRAINER vs. EaseVRx in decreasing pain interference, pain catastrophizing, anxiety, and self-efficacy. While the concepts measured are different, and the tests of change distinct, the analysis approach will be similar for all PROs. Independently for each PRO, a two-sample t-test will be used to compare differences-in-differences between the arms. Additionally, we will use an analysis of covariance (ANCOVA) to determine whether the average gain is different between the two groups after controlling for baseline-scores by including them as covariates. If assumptions of ANCOVA are not met, we will consider generalized linear models, including ordered logistic regressions to determine whether the proportional odds of average gain in the scale are different between the two groups after controlling for baseline-scores by including them as covariates.

Opioid Usage - The goal of this analysis is to test the effectiveness of PainTRAINER vs. EaseVRx in decreasing weekly average milligrams morphine equivalent (MME) of prescribed medication between the baseline week and the week before week 8. Weekly average MME will be calculated as a 7-day average of daily maximum MME as prescribed. Analysis of this endpoint will proceed via ANCOVA, adjusting for subjects' baseline MME. We will assess the assumptions underpinning the ANCOVA model graphically and will undertake appropriate transformation of the weekly average MME outcome as deemed appropriate. If no suitable transformations can be found, bootstrapped confidence intervals for the between-group differences in weekly MME will be produced.

Both adjusted and unadjusted between-group comparisons will be presented with 95% confidence intervals.

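### Section 4.1 describes 1:1 allocation by site, Section 6.3 names no site strata, and no primary or secondary analysis includes site; if site does stratify and predicts outcome, the tests are mildly conservative

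*Combined protocol and SAP*

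**What the plan says.** On design, Section 4.1 states that "patients will be allocated in a 1:1 ratio at the site level". The natural reading is that the arms are balanced within each site. Section 6.3, which sets out how allocation is done, says only that a random number generator will "assign every-other patient to blocks of 2, 5, or 6 to ensure there is an equal distribution" between the groups. It does not mention site or any other stratum. The synopsis (Section 1.1) lists "Four outpatient clinic sites, including Cedars-Sinai Medical Center" and three others, and adds: "In addition, participants may enroll remotely". Section 5.5 says the UAB coordinator also serves patients identified through Bendcare. No section says which stratum a remote or Bendcare patient belongs to.

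On analysis, the primary comparison in Section 9.4.2 is unstratified: "The between arm difference of achieving the MCID of 2 will be tested using Chi-squared test". The supporting logistic regression compares the arms "after accounting for baseline-scores by including them as one of the predictors"; no other predictor is named. For the secondary patient-reported outcomes, Section 9.4.3 says: "Independently for each PRO, a two-sample t-test will be used to compare differences-in-differences between the arms". The ANCOVA that follows, and its fallback models, name only the baseline score. The opioid (MME) ANCOVA names only baseline MME.

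Site appears in none of these. The nearest items are state and zip code among the candidate effect modifiers in the exploratory analysis (Section 9.4.7), and the unnamed baseline covariates behind the R² columns of Table 1 (Section 9.2).

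**The concern.** When arms are balanced within site, differences between sites cancel out of the treatment comparison, so the true error of the estimated effect contains little between-site variation. A test that leaves site out still counts that variation in its estimated error. The reported standard error is then too large, the confidence interval too wide, and the test rejects less often than its nominal level under the null.

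Site differences are plausible here. Section 5.5 describes rural populations that are nearly 32% non-Hispanic Black in Louisiana, 22.7% in Alabama and 2.5% in California, and Section 9.4.7 lists race, ethnicity and state as possible predictors of response. Plausible is as far as this goes, because the documents give no between-site figure for any outcome.

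What is at stake is a modest amount of precision, in a trial whose success depends on showing a difference, together with clarity about how patients were randomised.

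**Working it through.** **Inputs from the documents:** 150 patients per arm, SD 2, difference 0.75, 90% power, and Table 1 (Section 9.2); two-sided 0.05 (Section 9.4.1); four sites (Section 1.1); covariates as named in Sections 9.4.2 and 9.4.3.

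**Assumed, because the documents are silent:** how far sites differ in outcome, how many patients each contributes, and permuted blocks of 2, 4 and 6 in the simulation (a block of 5 cannot be split 1:1).

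**Step 1: the plan's own figures.**
- Means: SE = 2 × √(2/150) = 0.2309. Power = Φ(0.75/0.2309 − 1.96) = Φ(1.288) = 0.901. The noncentral t gives 0.899.
- Table 1 example: a response of 0.3 with odds ratio 2.25 gives 0.675/1.375 = 0.491 in the other arm. The effective size is 150 × (1 − 0.1) = 135 per arm, and the pooled two-proportion formula gives power 0.898. All 12 cells reproduce to within 0.005 in the odds ratio.

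The stated 90% power therefore stands without any reference to site.

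**Step 2: continuous outcomes, allocation balanced within site.** Let s be the share of variance due to site in the outcome as analysed. Then:
- true SE = unadjusted SE × √(1 − s);
- excess in the reported SE = 1/√(1 − s) − 1;
- true alpha = 2 × [1 − Φ(1.96/√(1 − s))];
- power without site = Φ((0.75 − 1.96 × 0.2309)/(0.2309 × √(1 − s)));
- power with site = Φ(0.75/(0.2309 × √(1 − s)) − 1.96).

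| s (assumed) | SE too large by | True alpha | Power without / with site |
|---|---|---|---|
| 0.01 | 0.5% | 0.049 | 0.902 / 0.904 |
| 0.02 | 1.0% | 0.048 | 0.903 / 0.907 |
| 0.05 | 2.6% | 0.044 | 0.907 / 0.915 |
| 0.10 | 5.4% | 0.039 | 0.913 / 0.928 |

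The gain from including site is about 0.2 to 1.6 power points. The power columns use the plan's NRS difference and SD as an illustration.

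**Step 3: the primary responder test.** The simulation had 300 patients in four sites, allocation stratified by site, control response about 0.3 and odds ratio 2.17 (the Table 1 value at R² = 0), with 20,000 runs. Monte Carlo error is about 0.0015 on alpha and 0.002 on power. Each pair of figures is chi-squared / Cochran-Mantel-Haenszel (CMH).

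| Site response rates (assumed) | Alpha, 4 × 75 | Power, 4 × 75 | Power, 130/80/60/30 |
|---|---|---|---|
| all equal | 0.050 / 0.050 | 0.905 / 0.904 | 0.906 / 0.905 |
| 0.25-0.35 | 0.050 / 0.050 | 0.897 / 0.898 | 0.894 / 0.895 |
| 0.20-0.40 | 0.048 / 0.050 | 0.890 / 0.894 | 0.874 / 0.880 |
| 0.10-0.50 | 0.036 / 0.047 | 0.828 / 0.859 | 0.780 / 0.816 |

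Compare within a cell, not down a column, because the overall effect itself changes with the spread. Stratifying gains nothing when sites are alike, about 0.1 to 0.6 points in the two middle rows, and 3 to 4 points in the last.

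**Step 4: allocation not stratified by site.** The same scenarios give a chi-squared type I error of 0.048 to 0.052, so the planned test holds its level.

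**The case against.** The strongest reply is that the premise rests on one phrase. Section 4.1 mentions site, but Section 6.3, where strata would be expected, does not. If allocation is not stratified, the planned test is valid as it stands (Step 4). This reply stands, and it makes the point conditional. It does not remove the point, because the two sections still have to be reconciled.

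A second reply is that site may not predict outcome. All the efficacy outcomes are changes from baseline or are adjusted for it, so stable site differences in level largely drop out, and differences in race mix or state do not show different response rates. This also stands. The loss may be nil.

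A third reply is that the logistic model's wording leaves room for further predictors. It does, but it does not prespecify site, and the chi-squared test and the t-tests have no covariates.

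A reader might infer three stronger things that the documents do not support:
- **That false-positive risk rises.** The error runs the other way: true alpha is at or below 0.05, apart from simulation noise.
- **That the 90% power is wrong.** It reproduces (Step 1).
- **That site adjustment would raise power substantially.** This impression comes from comparing the chi-squared test with a logistic model holding both baseline pain and site. A separate simulation took the contributions apart. It used 4,000 runs, 4 × 75 patients, an assumed effect of 0.9, SD 2, correlation 0.5, a control change of 1 point, and Monte Carlo error of about 0.5 points. With a site SD of 0.5, power was 84.9% for chi-squared, 85.6% with site only, 90.1% with baseline only and 91.0% with both. With a site SD of 0.8 the figures were 82.9%, 84.2%, 87.1% and 89.3%. Most of the combined gain belongs to baseline, which Section 9.4.2 already plans to adjust for in its additional model.

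**Conclusion.** The point holds in a limited, conditional form, with moderate confidence. It is certain that Section 4.1 places allocation at the site level, that Section 6.3 is silent on site, and that no primary or secondary analysis includes it. The statistical consequence follows only if site truly stratifies randomisation and sites differ in outcome. The planned tests are then mildly conservative and give up some precision. The loss is small at moderate site differences and reaches several power points only when site response rates spread very widely. Every size given rests on assumed between-site variation. This is a mismatch between described design and planned analysis that is worth correcting. It does not threaten the validity of the trial's conclusions.

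**What to change.** 1. Reconcile Sections 4.1 and 6.3: state whether randomisation is stratified by site. Correct the block size of 5 in the same edit, since it cannot give equal arms.
2. Define the stratum for patients who enrol remotely, and say whether Bendcare is its own stratum or belongs with UAB, with which it shares a coordinator.
3. If site does stratify, replace the chi-squared test with a Cochran-Mantel-Haenszel test stratified by the randomisation site, or with a logistic model containing site and baseline pain. Name one of these as primary.
4. In that case, also add site as a fixed factor to the ANCOVA for each secondary patient-reported outcome and for MME.
5. Fix a rule for pooling small strata before unblinding.

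The cost is wording only; no new data collection should be needed, since patients are identified and recruited through a site. The downside is that sparse strata may need pooling. In the simulations the CMH test cost at most about 0.1 power point when sites did not differ, which is within Monte Carlo error. If site does not stratify, correct Section 4.1; the chi-squared test can then stay on this ground.

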9.4.3 ANALYSIS OF THE SECONDARY ENDPOINT(S)

Pain Interference, Pain Catastrophizing, Coronavirus-Related Anxiety, and Self-Efficacy

The goal of these analyses is to test the difference in the effectiveness of PainTRAINER vs. EaseVRx in decreasing pain interference, pain catastrophizing, anxiety, and self-efficacy. While the concepts measured are different, and the tests of change distinct, the analysis approach will be similar for all PROs. Independently for each PRO, a two-sample t-test will be used to compare differences-in-differences between the arms. Additionally, we will use an analysis of covariance (ANCOVA) to determine whether the average gain is different between the two groups after controlling for baseline-scores by including them as covariates. If assumptions of ANCOVA are not met, we will consider generalized linear models, including ordered logistic regressions to determine whether the proportional odds of average gain in the scale are different between the two groups after controlling for baseline-scores by including them as covariates.

Opioid Usage - The goal of this analysis is to test the effectiveness of PainTRAINER vs. EaseVRx in decreasing weekly average milligrams morphine equivalent (MME) of prescribed medication between the baseline week and the week before week 8. Weekly average MME will be calculated as a 7-day average of daily maximum MME as prescribed. Analysis of this endpoint will proceed via ANCOVA, adjusting for subjects' baseline MME. We will assess the assumptions underpinning the ANCOVA model graphically and will undertake appropriate transformation of the weekly average MME outcome as deemed appropriate. If no suitable transformations can be found, bootstrapped confidence intervals for the between-group differences in weekly MME will be produced.

Both adjusted and unadjusted between-group comparisons will be presented with 95% confidence intervals.

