9.2 SAMPLE SIZE DETERMINATION

Sample Size calculations and Power Estimation

Sample Size calculations and Power Estimation

Sample Size Calculation: The primary goal of the study is to test the effectiveness of *PainTRAINER* vs. *EaseVRx*, in reducing pain intensity. The trial will be testing if there is statistical evidence that either *PainTRAINER* or *EaseVRx* is more effective in lowering average weekly pain intensity after 8 weeks from start of intervention. We estimate power to assess the effect of the

Table 1. Minimum detectable odds ratio as a function of the proportion of variability in treatment type that is explained by all other relevant covariates in the model and the baseline probability of positive treatment response.

Baseline probability	R ²			
	0.0	0.1	0.2	0.4
0.2	2.32	2.42	2.55	2.91
0.3	2.17	2.25	2.37	2.69
0.5	2.15	2.25	2.37	2.74

interventions on the treatment response (achievement of a minimally clinically important difference [MCID] of 2.0 on the NRS^{56,57} (y/n)) using logistic regression, accounting for possible confounding factors for the primary outcome described in Aim 1. The dependent variable is the treatment response and the main independent variable of interest is *PainTRAINER* vs. *EaseVRx*. **Table 1** displays the minimum odds ratio that can be detected with 90% power with the two-sided 0.05 level of significance as a function of baseline probability of positive response when a patient is treated with *EaseVRx* and R², the proportion of variability in the predictor of interest that is explained by all relevant baseline covariates in the model using data from 150 patients in the *PainTRAINER* arm and 150 in the *EaseVRx*. For example, data from 300 patients achieve 90% power to detect an odds ratio of 2.25 if the probability of positive response when a patient is treated with *PainTRAINER* is 0.3 and 0.1 of the variability in intervention is explained by all other baseline covariates in the model. These odds ratios vary between 2.15 and 2.91 and are clinically meaningful. Therefore, we have enough power to test statistical significance of predictors in the multivariable logistic regression model. Regarding clinical significance, given an MCID of 2 points on the NRS and a SD of 2 on this scale from our own digital health trials, data from 150 patients in each group

will achieve 90% power to detect a mean pain intensity score difference of 0.75, corresponding to a clinically meaningful effect size of 0.38 SD.

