9.4 STATISTICAL ANALYSES

9.4.1 GENERAL APPROACH

All statistical analyses will be performed jointly by the Cedars-Sinai Biostatistics Core and the Cedars-Sinai Center for Outcomes Research and Education (CS-CORE) using SAS® software version 9.3 or higher (SAS Institute, Cary, NC, USA), R version 3.5.0 or higher (R Foundation for Statistical Computing, Vienna, Austria) or Stata software version 14 or higher (StataCorp LLC, College Station, TX, USA). Continuous variables will be summarized using descriptive statistics (N, mean, standard deviation, minimum, median, and maximum as appropriate). Categorical variables will be summarized using the number and percentage of patients in each category. Data will be summarized with respect to patient demographic and baseline characteristics both across the study and by study-arm. The efficacy endpoints, safety assessments, and other outcome results for each treatment group will be summarized descriptively unless otherwise indicated. In addition, statistical model estimates of least squares means, treatment differences, p-values and 95% confidence intervals will also be provided where relevant. The fit of general linear models will be assessed using residual plots and/or other diagnostic plots as appropriate. The fit of logistic models will be assessed using Hosmer-Lemeshow goodness-of-fit and/or receiver operating characteristic (ROC) curves as appropriate. All statistical tests will be 2-sided and performed at the 0.05 level of significance unless stated otherwise.

Multiple Comparisons/Multiplicity: The family-wise type I error rate (FWER) for the statistical tests of the primary and secondary endpoints will be controlled at 0.05. To strongly control the FWER at this level, a gatekeeping approach will be utilized. A closed testing procedure will be employed to control the FWER. Any hypothesis tests conducted for model building purposes will be conducted outside of any gatekeeping.

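### The primary and four PRO scales each get an unadjusted and a baseline-adjusted test with neither named as deciding, so the promised 0.05 error control is not guaranteed as written

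*Combined protocol and SAP*

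**What the plan says.** **Primary (9.4.2).** Responder status, meaning an improvement of at least 2 NRS points, is compared between arms by chi-squared. A further bullet reads "Additionally, we will use a logistic regression to determine whether the odds of achieving the MCID of 2 is different between the two groups", with the baseline score as a predictor. The success criterion asks only for statistical evidence that one program is better.

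**Four PRO scales (9.4.3).** For pain interference, catastrophizing, anxiety and self-efficacy: "Independently for each PRO, a two-sample t-test will be used to compare differences-in-differences between the arms". An ANCOVA adjusted for baseline is then added. If its assumptions are not met, generalized linear models, including ordered logistic regression, may be considered. The section closes with "Both adjusted and unadjusted between-group comparisons will be presented with 95% confidence intervals".

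**Opioid use (9.4.3).** ANCOVA on baseline MME is the named analysis.

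**Error control (9.4.1).** "The family-wise type I error rate (FWER) for the statistical tests of the primary and secondary endpoints will be controlled at 0.05". The means are described as "a gatekeeping approach will be utilized. A closed testing procedure will be employed to control the FWER". Also: "All statistical tests will be 2-sided and performed at the 0.05 level of significance unless stated otherwise". No endpoint order is given, and no rule covers two tests of the same endpoint.

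**Power (9.2).** The responder calculation rests on covariate-adjusted logistic regression, not on chi-squared.

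**The concern.** A closed or gatekept procedure needs one valid level-0.05 test for each hypothesis. Here the primary, which is the natural gate, and four secondary endpoints each produce two p-values. The plan does not say which one opens the gate or supports a claim. Sections 9.2 and 9.4.2 also point different ways: power rests on an adjusted model, while the unadjusted test is listed first.

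Two different harms are possible, depending on how the text is read. If a result on either test can be claimed, type I error for that endpoint exceeds 0.05. If the first-listed test decides, error is held, but the four PROs are judged by an analysis that makes poorer use of a baseline already collected before randomization.

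**Working it through.** **Inputs from the documents.** Two-sided 0.05 (9.4.1); 1:1 allocation (4.1: "patients will be allocated in a 1:1 ratio at the site level"); 150 per arm (9.2: "data from 150 patients in each group"); NRS SD of 2 and a 0.75-point difference (9.2).

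**Assumed, because the documents do not give it.** The baseline to Week 8 correlation r. Baseline and Week 8 SDs are taken as equal, with no dropout.

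**1. The plan's own figures.** z = 0.75 / (2 × √(2/150)) = 0.75 / 0.2309 = 3.248. Power = Φ(3.248 − 1.960) = 0.901, so the stated 90% is reproduced. The 12 odds ratios in Table 1 give power of 0.898 to 0.902, so that table is reproduced as well.

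**2. Four PROs.** In units of the SD squared, the per-patient variance is 2(1 − r) for change and 1 − r² for ANCOVA.

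- Variance ratio, ANCOVA to change score: (1 − r²) / [2(1 − r)] = (1 + r)/2.
- Correlation of the two z-statistics under no effect: √((1 + r)/2).
- The chance that at least one |z| exceeds 1.96 follows from the bivariate normal. It was confirmed with 40,000 simulated null trials per value of r.

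| r | Correlation of z | Either test significant | Both significant | Variance ratio | Power at 0.3 SD: t-test / ANCOVA |
|---|---|---|---|---|---|
| 0.3 | 0.81 | 7.8% | 2.2% | 0.65 | 60% / 78% |
| 0.5 | 0.87 | 7.3% | 2.7% | 0.75 | 74% / 85% |
| 0.7 | 0.92 | 6.8% | 3.2% | 0.85 | 92% / 95% |

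Power check at r = 0.5:

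- t-test: 0.3 / √(2 × 1.00/150) = 0.3 / 0.1155 = 2.60, and Φ(2.60 − 1.96) = 0.74.
- ANCOVA: 0.3 / √(2 × 0.75/150) = 0.3 / 0.1000 = 3.00, and Φ(3.00 − 1.96) = 0.85.

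At r = 0.9 the either-test error falls to 5.8% and the variance ratio rises to 0.95. Each test used alone held its level: 0.048 to 0.050 for the t-test and 0.048 to 0.051 for ANCOVA.

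**3. Primary.** This used 10,000 simulated null trials per correlation. Assumptions: baseline NRS roughly normal (mean 5.5, SD 2, truncated above 3), mean improvement of 1 point in both arms, and a response rate of 23% to 35%.

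| r | Chi-squared | Adjusted logistic | Either | Both |
|---|---|---|---|---|
| 0.4 | 4.8% | 5.0% | 6.8% | 3.1% |
| 0.6 | 5.3% | 5.2% | 6.7% | 3.8% |
| 0.8 | 4.8% | 4.7% | 5.6% | 4.0% |

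Two independent tests would give 1 − 0.95² = 9.75%. The actual pairs stay well below that because their statistics are highly correlated.

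**The case against.** The best defense is that the plan already ranks the tests. Chi-squared is the test attached to the primary outcome and the t-test is the one attached to each PRO; the adjusted models come second, as additions. The closing sentence of 9.4.3 concerns reporting and is not a decision rule. On that reading the pairing inflates nothing.

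Much of this stands. The documents state no either-test rule, so a reader who infers that error control fails outright goes further than the text allows. The ranking is only implied, however, and 9.2 points to the adjusted model for the primary. The text therefore does not settle the matter. Accepting the implied ranking also does not rescue the PROs, because the less precise test then decides.

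Three other tempting readings do not hold:

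- **Both harms at once.** They are alternatives. Inflation needs an open choice of test; the loss of precision needs the first-listed test to decide.
- **A precision loss for the primary.** The variance argument is exact for the t-test against ANCOVA only. Chi-squared and logistic regression do not share an estimand. At r = 0.4 the simulated standard error of the log odds ratio is larger after adjustment (0.264 against 0.242), because the conditional odds ratio is a different quantity.
- **Every self-reported endpoint.** Opioid use is self-reported, but its analysis is already named as ANCOVA.

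It is also fair to say that the missing endpoint order in 9.4.1 is a wider gap, of which this is one part, and that the plan makes no power claim for the four scales.

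**Conclusion.** The point holds in a limited form and should be fixed. For the primary and the four PRO scales the plan names no deciding test, so the strong 0.05 control promised in 9.4.1 cannot be verified from the text.

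If either result may count, the excess is modest: about 2 to 3 percentage points per PRO for r between 0.7 and 0.3, and about 0.6 to 1.8 points for the primary under the simulation's assumptions. If the first-listed test decides, there is no excess, but at r = 0.5 the change-score analysis needs 1/0.75 = 1.33 times the patients that ANCOVA needs for the same precision.

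The PRO figures depend on an assumed correlation, equal SDs, no dropout and, for power, an assumed 0.3 SD effect.

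**What to change.** - **9.4.3:** name ANCOVA adjusted for baseline as the single deciding test for each of the four PROs, and label the t-test on change as a sensitivity analysis.
- **9.4.2:** name the baseline-adjusted logistic regression as the single deciding test for the primary. This is the type of model on which 9.2 bases the responder power. Label chi-squared as a sensitivity analysis.
- **Fallback in 9.4.3:** state that any ordered logistic model used when ANCOVA assumptions look poor is supportive only and does not replace the deciding test. Otherwise the deciding test, and the quantity it estimates, could change after the data are seen.
- **9.4.1:** state that the gatekeeping and closed testing procedure uses only these deciding tests. The endpoint order still has to be supplied separately.

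Both adjusted and unadjusted results can still be reported. The cost is a few sentences in the analysis plan, written before unblinding; no new data and no extra patients are needed.
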